### **7.2.3. Reporting of Serious Adverse Events**

Every SAE, regardless of the causal relationship to the study treatment, occurring after the patient has signed informed consent, until at least 30 days after the patient has stopped study treatment, must be reported to the HCTU Quality Team and Karyopharm Pharmacovigilance Department within *24 hours* of learning of its occurrence. The investigational site personnel must use the SAE Report Form provided by Karyopharm for reporting any SAE to the Karyopharm Pharmacovigilance Department ([Appendix 1](#)).

Upon completion, the SAE Report Form must be immediately emailed or faxed to:

Pharmacovigilance Department

Karyopharm Therapeutics Inc.

Email: [[contact]](mailto:[contact]) and [[contact]](mailto:[contact])

[contact] (USA)

Any SAE observed after the 30-day follow-up period should only be reported to HCTU Quality Team and Karyopharm if the Investigator suspects that the SAE has causal relationship to the Karyopharm study drug. Recurrent episodes, complications, or progression of the initial SAE must be reported as follow-up to the original episode within 24 hours of the Investigator receiving the follow-up information.

An SAE should be followed until its resolution or until it is judged to be permanent, and assessment should be made at each visit (or more frequently, if necessary) of any changes in severity of the event, the suspected relationship to the study treatment, the interventions required to treat the event, and the outcome.

Sponsor-Investigator is responsible as applicable for notifying their appropriate Health Authorities, Institutional Review Board, Local and Central Ethics Committees (EC) and Food and Drug Administration of all SAEs in accordance with regulations.

### **7.2.4. Suspected Unexpected Serious Adverse Reactions**

Suspected unexpected serious adverse reactions (SUSARs) are SAEs that are unexpected (per the current version of the IB) and judged by the Sponsor-Investigator or Karyopharm to be related to the Karyopharm study drug administered. All SUSARs will be collected and reported to the competent authorities and relevant ethics committees in accordance with the FDA's "Safety Reporting Requirements for Investigational New Drugs and Bioanalytical/Bioequivalence Studies" (FDA 2012).

### 7.2.5. Adverse Event Reporting

The Investigator will report all AEs (including all non-serious AEs) to Karyopharm Pharmacovigilance twice per year in the form of line-listings in an excel spreadsheet.

Karyopharm, the drug supplier, will supply the cut-off dates of each requested line listing. The line listings will contain the following information: study ID, unique subject ID, adverse event term, serious event (yes or no), onset date (complete or partial), end date (complete or partial), action taken with KPT-9274, causality to KPT-9274, event ongoing (yes or no), outcome of AE, severity CTCAE Grade (1-5), subject dosed with KPT-9274 (yes or no), date of first dose of KPT-9274, preferred term, system organ class (optional)

See the excel spreadsheet template in [Appendix 4](#).

## 7.3. Procedures for Handling Special Situations

### 7.3.1. Pregnancy

Note: Pregnancy *per se* is not considered to be an AE; however, it is discussed here because of the importance of reporting pregnancies that occur during studies and because a medical occurrence observed in the mother or fetus/newborn would be classified as an AE.

Female patients of childbearing potential and fertile male patients will be informed as to the potential risk of conception while participating in this study and will be advised that they must use highly effective contraception listed below (ie, results in a low failure rate when used consistently and correctly) during the dosing period and for a period of at least 3 months after the end of treatment.

A list of highly effective methods of contraception is provided in Section 5.7.

A pregnancy test will be performed on each premenopausal female patient of childbearing potential prior to the first dose of study drug, on Day 1 of Cycles  $\geq 2$  while on treatment, and again at treatment discontinuation during the End-of-Treatment visit. A negative pregnancy test must be documented prior to administration of study drug.

If a patient is confirmed pregnant during the study, study drug administration must be discontinued immediately. The Investigator must immediately notify the Sponsor investigator of this event and record the Pregnancy on the Pregnancy Form. The initial information regarding a pregnancy must be forwarded to Karyopharm's Pharmacovigilance Department by email or fax within 24 hours of first knowledge of its occurrence. A pregnancy report form is provided by Karyopharm Pharmacovigilance.

The pregnancy should be followed up to determine the outcome, including spontaneous or voluntary termination, details of the birth, and the presence or absence of any birth defects, congenital abnormalities, or maternal and/or newborn complications.

All pregnancies occurring within 3 months after the patient's last dose of study drug must be reported to Karyopharm, regardless of whether the patient received the Karyopharm study drug or other study drugs, withdraws from the study, or the study is completed. Patients should be instructed to inform the Investigator regarding any pregnancies.

Any SAE that occurs during pregnancy must be recorded on the SAE report form (eg, maternal serious complications, therapeutic abortion, ectopic pregnancy, stillbirth, neonatal death, congenital anomaly, or birth defect) and reported within 24 hours in accordance with the procedure for reporting SAEs (described in Section 7.2).

A pregnancy in a female partner of a male patient must be reported to Karyopharm Pharmacovigilance within 24 hours of learning of its occurrence. Pregnancies in female partners should only be followed if the male patient is being treated with a KPT-9274-containing regimen. Consent to report information regarding these pregnancy outcomes should be obtained from the female partner.

It is not known whether KPT-9274 passes into the breast milk. Mothers should not breastfeed while being treated with a KPT-9274-containing regimen and for 2 weeks after the last dose.

## 8. STATISTICAL METHODS

### 8.1. General Considerations

Tabulations will be produced for appropriate disposition, demographic, baseline, efficacy, and safety parameters. For categorical variables, summary tabulations of the number and percentage of patients within each category (with a category for missing data) of the parameter will be presented. For continuous variables, the number of patients, mean, median, standard deviation, minimum, and maximum values will be presented. Time-to-event data will be summarized using Kaplan-Meier methodology with median event time and associated 2 sided 95% confidence intervals, as well as number and percentage of patients with events and censored patients.

Patients who are in the Dose Escalation Phase being treated at the RP2D chosen for expansion will be included in the efficacy and safety assessment of the Dose Expansion Phase.

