### 5.2.6. Dose Escalation Guidelines

#### 5.2.6.1. Dose Escalation Procedures

For the purposes of dose escalation decisions, a standard 3+3 dose escalation design will be used.

The initial cohort, Cohort 1, will consist of 3 enrolled patients who will be treated at 30 mg. If these patients do not experience a DLT during Cycle 1, the KPT-9274 dose will be escalated to 40 mg for another group of 3 patients (Cohort 2). If the MTD is exceeded at cohort 1, de-escalation to cohort 0 (20 mg) will occur. If the MTD is not exceeded in cohort 1, dose escalation will continue based on a standard 3+3 design at the dose levels specified in

Table 8.

A RP2D equal to or less than the MTD will be declared at the conclusion of the dose escalation, and potentially used for the Dose Expansion Phase. The RP2D will be based on an evaluation of any and all pharmacokinetic, pharmacodynamic and safety data, including an evaluation of SAEs that occur after the end of the DLT window to ensure the tolerability of the RP2D. The MTD is defined as the highest dose at which  $\leq 1$  patient experiences a DLT in Cycle 1.

Patients must complete a minimum of 1 cycle of treatment, defined as receiving  $\geq 75\%$  of KPT-9274 doses during Cycle 1 (e.g.,  $\geq 9$  of 12 doses in the 3 doses/week schedule), or have a DLT within the first cycle of treatment to be evaluable for dose escalation decisions. Dose escalation decisions will occur when the cohort of patients has met these criteria.

Dose escalation will be conducted as follows:

- If 0 of 3 patients experiences a DLT, escalate to next higher dose cohort.

- If 1 of 3 patients experiences a DLT, that cohort will be expanded to 6 patients. If 1 of 6 patients experiences a DLT, escalate to the next higher dose cohort;
- If  $\geq 2$  of 3 or  $\geq 2$  of 6 patients experience a DLT, MTD is exceeded. If the MTD is exceeded, the patients will be de-escalated to the next lower dose level (the MTD).

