### 5.2.7. Dose Schedule for Evaluation During the Dose Expansion Phase

After completion of the Dose Escalation, Dose Expansion in up to 10 additional patients who meet the inclusion/exclusion criteria may be conducted to further explore safety, tolerability and preliminary evidence of anti-tumor activity of the RP2D of KPT-9274.

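### Pooling escalation patients at the RP2D into the expansion safety summary biases the first-cycle DLT proportion low on average, and no split by phase is planned

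*Combined protocol and SAP*

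**What the plan says.** Section 8.1 (General Considerations) sets the pooling rule for the expansion phase: "Patients who are in the Dose Escalation Phase being treated at the RP2D chosen for expansion will be included in the efficacy and safety assessment". Section 5.2.7 says that the expansion "may be conducted to further explore safety, tolerability and preliminary evidence of anti-tumor activity of the RP2D", so tolerability is one of its purposes, although the expansion objective and endpoints listed in the synopsis and in Section 1 concern efficacy.

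Section 5.2.6.1 sets the selection rule. The design is a 3+3 ("For the purposes of dose escalation decisions, a standard 3+3 dose escalation design will be used"). A dose clears in one of two ways: "If 0 of 3 patients experiences a DLT, escalate to next higher dose cohort", or, after the cohort is enlarged, "If 1 of 6 patients experiences a DLT, escalate to the next higher dose cohort". Two or more DLTs fail the dose ("6 patients experience a DLT, MTD is exceeded"). Then "A RP2D equal to or less than the MTD will be declared at the conclusion of the dose escalation". DLTs are not the only ground for the choice: "The RP2D will be based on an evaluation of any and all pharmacokinetic, pharmacodynamic and safety data", and the same sentence adds SAEs after the DLT window.

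Sections 8.3.2 and 8.6 run safety analyses on all treated patients, and Section 8.6 lists DLTs among the safety measures. Section 8.6.1 tabulates TEAEs without hypothesis tests and without a stated split by dose or phase. Section 8.4 promises by-patient listings of all eCRF data. Nowhere is there an expansion-only safety table, a split by phase, or a note about the selection.

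**The concern.** If the RP2D is a dose studied in escalation (otherwise there is nobody to pool), its cohort enters the expansion summary only because it had at most one DLT. The newly enrolled patients are under no such condition. Adding the two groups together mixes a part that was filtered for few DLTs with a part that was not, and the combined DLT proportion falls below the true rate on average.

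At stake is how a reader judges the tolerability of the RP2D. In percentage points, the shortfall grows with the true rate over the range examined below. The pooled figure is therefore furthest from the truth when the chosen dose is more toxic than it looked.

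**Working it through.** **Plan's own figures.** The documents state no DLT rate, so there is none to reproduce. The cohort and expansion sizes used below do reproduce the enrolment totals: 4 × 6 + 10 = 34 (Section 8.2.1), and 5 × 6 + 10 = 40 (synopsis).

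**Inputs.** From the documents: the clearing outcomes 0/3 and 1/6 (Section 5.2.6.1), and up to 10 expansion patients (Section 8.2.1). Assumed: a true first-cycle DLT rate p at the RP2D of 10%, 20% or 30%, all patients evaluable for DLTs, outcomes independent, and no further selection on other data.

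**Step 1: probability of each clearing outcome.**
- 0/3: (1−p)³
- 1/6: 3p(1−p)² × (1−p)³

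At p = 0.20 these are 0.512 and 0.384 × 0.512 = 0.197, in total 0.709. Given that the dose cleared, the outcome is 0/3 with probability w = 0.512/0.709 = 0.7225, and 1/6 with probability 0.2775. Failure of the next dose up does not alter these weights, because those patients are independent.

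**Step 2: expected DLT proportions given clearance.**
- Escalation cohort alone: (1−w)/6. At p = 0.20: 0.2775/6 = 4.6%.
- Pooled with 10 expansion patients: w × 10p/13 + (1−w) × (1+10p)/16. At p = 0.20: 0.7225 × 2/13 + 0.2775 × 3/16 = 0.1112 + 0.0520 = 16.3%.
- Expansion alone: p, hence unbiased.

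| True rate p | Dose clears | w | Escalation cohort | Pooled | Bias (points) | Relative |
|---|---|---|---|---|---|---|
| 10% | 0.906 | 0.8045 | 3.3% | 8.6% | −1.4 | −14% |
| 20% | 0.709 | 0.7225 | 4.6% | 16.3% | −3.7 | −18% |
| 30% | 0.494 | 0.694 | 5.1% | 23.7% | −6.3 | −21% |

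At 5% the bias is −0.5 points, and at 40% it is −9.1.

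**Step 3: sensitivity.** With only 5 expansion patients the pooled averages are 7.7%, 14.1% and 20.0%. If the RP2D cohort always had 6 patients with at most one DLT (10 in expansion), they are 8.8%, 16.3% and 23.3%. Whole trials were also simulated (200,000 per curve, RP2D set equal to the MTD) under four assumed dose-toxicity curves. The average true rate at the selected dose was 15.3%, 19.6%, 20.5% and 24.7%, against pooled averages of 12.7%, 15.9%, 16.5% and 19.8%, a bias of −2.6 to −5.0 points.

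**Step 4: other adverse events.** If an event occurs with probability a₁ in patients with a DLT and a₀ in those without, its pooled bias is (a₁ − a₀) times the DLT bias. With a₁ = a₀ it is zero. With a₀ = 81.7% (borrowed as an illustration from the anemia frequency in Section 1.2.1) and a₁ = 100%, it is 0.183 × 1.4 to 0.183 × 6.3, that is, 0.3 to 1.2 points low. With 40% and 80% it is 0.4 × 1.4 to 0.4 × 6.3, that is, 0.6 to 2.5 points low.

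**Step 5: precision.** The standard error from expansion alone is √(p(1−p)/10): 9.5, 12.6 and 14.5 points at 10%, 20% and 30%. The root mean squared error of the pooled proportion, bias included, is 7.4, 10.1 and 12.3 points.

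**The case against.** The strongest reply is that pooling is a reasonable trade. The pooled proportion has the smaller root mean squared error at every assumed rate from 5% to 40%, and the expansion is optional and may enrol fewer than 10. At a true rate of 20% the expected shortfall is about half of one DLT: the selected cohort would hold 0.7225 × 0.6 + 0.2775 × 1.2 = 0.77 expected DLTs without selection, against 0.28 with it, among about 14 patients in all. Nothing turns on the figure: the MTD comes from escalation DLTs, AE rates are not tested, and no stopping rule uses the pooled rate. The split can also be recovered, since declaring the MTD requires DLT counts by cohort and patient listings are planned.

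Most of this stands, and it is a good reason to keep the pooled summary. It also rules out making expansion-only results the main estimate, which a reader might otherwise think follows. It does not justify showing the pooled figure alone. Better precision does not tell a reader that the estimate is shifted in a known direction, and rebuilding TEAE tables from listings is work that the plan could do itself.

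A reader might also infer that toxicity at the RP2D is understated in general. The documents do not support that. Section 8.6.1 tabulates all TEAEs through 30 days after the last dose, and events unrelated to DLTs carry no bias. Nor was the dose chosen on DLTs alone: a low count is necessary, but PK, PD and later safety data enter too. Selection on later SAEs could push in the same direction, but its effect cannot be quantified from the documents.

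**Conclusion.** The point holds in limited form. The pooled first-cycle DLT proportion at the RP2D is biased low by about 1.4 to 6.3 points on average for assumed true rates of 10% to 30% with 10 expansion patients. The shortfall is larger with fewer expansion patients. Events closely tied to DLTs share part of the bias. This is an expectation over repeated trials, not a certain result in this one, and it is smaller than the sampling error of 10 patients. The 4.6% shown by a cleared cohort at a true 20% describes the escalation part alone and should not be read as the size of the error in the pooled summary.

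The direction follows from the clearing rule in Section 5.2.6.1. The size depends on DLT rates that the documents do not give.

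One related gap is open. Section 2.1 lets patients at lower doses change to the RP2D (the synopsis says the MTD; the two should be reconciled), and Section 8.1 does not say whether they then count as treated at the RP2D for safety. They have already tolerated treatment, so counting them could add to the bias.

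This is a worthwhile improvement to reporting, not a flaw in the trial's decisions.

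**What to change.** Keep the pooled summary. In Sections 8.1 and 8.6:
- Present DLTs and TEAEs at the RP2D side by side for escalation patients, expansion patients and both pooled.
- State that the escalation cohort was selected on its DLT count, so that its DLT proportion, and the pooled one, are expected to be low.
- State whether patients who changed from a lower dose to the RP2D are counted, and in which column.

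The cost is extra table columns and a few sentences, with no new data or patients. The expansion-only column will be less precise, with at most 10 patients against up to 16 pooled (6 + 10), and should be read with that in mind.

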### 8.2. Determination of Sample Size

#### 8.2.1. Sample size

The sample size for the Dose Escalation Phase is based on a standard 3+3 design for the purpose of determining the RP2D and MTD. Each cohort will consist of 3 or 6 patients per cohort.

For the Dose Expansion Phase, up to 10 additional patients may be enrolled at the RP2D for KPT-9274

Assuming that 4 dose levels of KPT-9274 are evaluated during the Dose Escalation Phase and up to 10 additional patients are enrolled in the Dose Expansion Phase, the total combined enrollment is estimated to be at most 34 patients.

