**Number of Patients (planned):**

As many as 40 patients may be enrolled, a maximum of 30 in the dose escalation and 10 in the expansion. However, the number of patients required for completion of study enrollment cannot be defined *a priori* since this depends on the MTD.

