## 2. INVESTIGATIONAL PLAN

### 2.1. Overall Study Design and Plan

This is a first-in-disease, single-center, open-label dose escalation clinical study to assess preliminary safety, tolerability, and efficacy of KPT-9274, a dual inhibitor of PAK4 and NAMPT, in patients with relapsed or refractory AML for whom all standard therapeutic options considered useful by the investigator have been exhausted.

During dose escalation, patients will receive oral KPT-9274 three times a week every other day (Days 1, 3, 5, 8, 10, 12, 15, 17, 19, 22, 24, and 26) during each 28-day cycle, and the first dose cohort will be 30 mg. Subsequent dose escalation cohorts, as well as a de-escalation cohort, will be administered per the table below. Dose escalation will continue until the MTD is determined. The MTD is defined as the highest dose at which  $\leq 1$  patient experiences a DLT in Cycle 1. A RP2D equal to or less than the MTD will be declared and used for the Dose Expansion Phase, if conducted.

Patients must complete a minimum of 1 cycle of treatment, defined as receiving  $\geq 75\%$  of KPT-9274 doses during Cycle 1 (e.g.,  $\geq 9$  of 12 doses in the 3 doses/week schedule), or have a DLT within the first cycle of treatment to be evaluable for dose escalation decisions. The cycle length is 28 days the DLT period is the first 28 days of cycle 1. Dose escalation decisions will occur when a cohort of patients has met these criteria.

After the RP2D is determined, a dose expansion phase, of up to 10 additional patients, might be conducted, in which a preliminary determination of efficacy will be conducted, using the ELN criteria (Appendix 2). After the RP2D has been established, subjects at lower dose Cohorts may have the option to change dose to the RP2D, per investigator discretion.

Screening will be performed within 30 or 14 days prior to the start of therapy (i.e., Day -30 to Day -1, or Day -14 to Day -1), as summarized in Table 1. The Follow-up period includes the EOT visit, the Safety Follow-up visit, and Durability of Response and Survival Follow-up; see Table 3 for assessments to be completed during the Follow-up period.

The number of patients required for completion of study enrollment cannot be defined *a priori* since this depends on the number of patients needed for the dose escalation; but the maximum number of patients from the escalation and expansion cohorts will be 40.

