**Table 5 KPT-9274 Dose Escalation Levels*****KPT-9274 Dose Escalation Levels***

Cohort	KPT-9274
	Days 1, 3, 5, 8, 10, 12, 15, 17, 19, 22, 24, 26 in a 28-day cycle
0 (de-escalation, if needed)	20 mg
1 (starting cohort)	30 mg
2	40 mg
3	60 mg
4	80 mg
5	100 mg

Three patients will be enrolled in each cohort, if 1 of 3 patients in a cohort experiences a DLT, the number of patients in that cohort will be expanded to 6 patients. A maximum of 6 patients will be enrolled per cohort. The MTD is defined as the highest dose at which  $\leq 1$  patients out of a maximum potential cohort of 6 experiences a DLT.

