### 8.6. Safety Analysis

All safety analyses will be made on the Safety Population.

The safety and tolerability of KPT-9274 will be evaluated by means of DLTs, AE reports, physical examination results, electrocardiogram results and laboratory safety evaluations. NCI CTCAE, Version 5.0 will be used for grading of AEs.

The MTD will be based on the assessment of DLTs during the first cycle of therapy and will be defined as the highest dose at which  $\leq 1$  patient experiences DLTs within Cycle 1.

Interim safety data will be examined on an ongoing basis to ensure patient safety.

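### Section 8.2.1 gives at most 34 patients where the dose tables and two other sections imply 40, and the wording on the MTD label, the cohort cap and the dose-change target also conflicts between sections

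*Combined protocol and SAP*

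**What the plan says.** **Size.** Section 8.2.1 reads "Assuming that 4 dose levels of KPT-9274 are evaluated during the Dose Escalation Phase", with up to 10 expansion patients, and concludes that "the total combined enrollment is estimated to be at most 34 patients". The dose tables (synopsis, Section 2.1, Table 5) list Cohorts 1 to 5, from 30 to 100 mg, plus a de-escalation Cohort 0 at 20 mg. The synopsis states "As many as 40 patients may be enrolled, a maximum of 30 in the dose escalation and 10 in the expansion", and Section 2.1 that "the maximum number of patients from the escalation and expansion cohorts will be 40". Both add that the number needed cannot be fixed in advance.

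**MTD label.** Section 5.2.6.1 says "If the MTD is exceeded, the patients will be de-escalated to the next lower dose level (the MTD", closing the parenthesis there, and "If the MTD is exceeded at cohort 1, de-escalation to cohort 0 (20 mg) will occur". Section 8.6 says "The MTD will be based on the assessment of DLTs during the first cycle of therapy"; Table 5 and Section 5.2.6.1 likewise define the MTD as the highest dose with no more than one patient having a DLT.

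**Cap.** The synopsis and the text under Table 5 state "A maximum of 6 patients will be enrolled per cohort". Section 2.2 provides that a new patient in the same cohort will be considered when too few are evaluable. Sections 5.2.6.1 and 8.3.3 count evaluable patients: at least 9 of 12 doses in Cycle 1, or a DLT.

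**Dose change.** The synopsis lets patients at lower doses change to the MTD; Section 2.1 says the RP2D. Section 5.2.6.1 allows the RP2D to be below the MTD.

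**The concern.** A reader of the statistical section takes away a ceiling that the design section and the synopsis contradict. No rule in the plan stops escalation at four levels.

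The MTD is the primary objective and bounds the RP2D. When a level above Cohort 1 is exceeded, the level below has already been assessed, so the parenthetical label has DLT data behind it. When Cohort 1 is exceeded, the level below is Cohort 0, where no patient in this trial has yet been evaluated. Nor does the plan say what is reported if Cohort 0 also has two or more DLTs. Section 4.1 allows the sponsor to stop the study but does not define that result.

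The cap matters when an expanded cohort has one DLT and a non-evaluable patient. The decision rules are written for 1 of 6 and 2 of 6, and the sixth evaluable patient cannot be enrolled within the cap. Section 2.2 also requires replacement of some expansion patients, so the same question arises once the tenth has been enrolled.

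The dose-change conflict reaches the analysis. Section 8.3.1 defines the efficacy population by receipt of at least one dose of the RP2D chosen for expansion, so the dose to which patients change can affect who enters it.

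**Working it through.** **1. Size.** Inputs: up to 6 per cohort and 10 in expansion (8.2.1), four levels (8.2.1), five levels from the start (dose tables).

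- Plan's own figure: 4 × 6 + 10 = 34. Reproduced.
- Five levels: 5 × 6 + 10 = 30 + 10 = 40. This matches the synopsis and Section 2.1.
- Difference: 40 − 34 = 6, and 6/40 = 15%.

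**2. Chance of reaching the Cohort 0 branch.** Let p be the DLT risk at 30 mg, with independent patients, all evaluable. The plan gives no value for p, so a range is assumed. A level is cleared by 0 of 3, or by 1 of 3 followed by 0 of the next 3:

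P(exceeded) = 1 − (1−p)³ − 3p(1−p)⁵

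| p (assumed) | (1−p)³ | 3p(1−p)⁵ | P(Cohort 1 exceeded) |
|---|---|---|---|
| 5% | 0.8574 | 0.1161 | 2.7% |
| 10% | 0.7290 | 0.1771 | 9.4% |
| 15% | 0.6141 | 0.1997 | 18.6% |
| 20% | 0.5120 | 0.1966 | 29.1% |

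**3. Cap against replacement.** Let q be the chance that a patient is non-evaluable (not given in the plan; assumed) and p the DLT risk among evaluable patients. Enrolment stops at six, and replacement is allowed within that limit. The cohort is stuck if six are enrolled, k = 3, 4 or 5 are evaluable, and there is exactly one DLT, falling among the first three evaluable patients (otherwise 0 of 3 would already have cleared the level):

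P(stuck) = Σ over k = 3, 4, 5 of C(6,k)(1−q)ᵏq⁶⁻ᵏ × 3p(1−p)ᵏ⁻¹

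For q = 10% the weights for k = 3, 4, 5 are 0.0146, 0.0984 and 0.3543. At p = 0.215, where the sum is largest, the terms are 0.0058 + 0.0307 + 0.0868 = 0.123.

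| q (assumed) | Maximum over p | p at maximum | At p = 5% | At p = 10% |
|---|---|---|---|---|
| 10% | 12.3% | 0.215 | 5.8% | 9.5% |
| 20% | 20.6% | 0.233 | 9.1% | 15.1% |
| 30% | 25.2% | 0.252 | 10.4% | 17.5% |

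These are per opened cohort. Cohorts decided by a second DLT are not counted, nor are those with fewer than three evaluable patients, which have not reached the expansion rule.

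**4. Dose change.** No arithmetic applies. The synopsis names the MTD, Section 2.1 names the RP2D, and Section 5.2.6.1 allows the RP2D to be lower. If the change is to the RP2D, a patient from a lower cohort who changes receives that dose and meets the wording of Section 8.3.1. If it is to a higher MTD, the change itself does not bring that patient in.

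**The case against.** **On size.** Section 8.2.1 is a conditional estimate, and 34 is right for its condition. The firm maximum is stated twice, consistently, as 40. This stands to the extent that there is no arithmetic error and nothing operational follows. A reader might infer that the trial will overrun its planned size. The documents do not support that: 40 is an explicit limit, and passing 24 in escalation requires most cohorts to fill to six. What remains is that the four-level assumption and the words at most agree with no other section.

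**On the label.** A reader might infer that the plan would declare an untested dose to be the MTD. Other text points against this. The synopsis says that escalation or de-escalation continues until the MTD is determined, the dose tables include Cohort 0, and the accompanying text enrols three patients in each cohort. Loose wording is the likelier explanation. Moreover, untested here means within this trial: Section 1.3.1 reports that the earlier solid tumor study escalated from 10 to 40 mg. The objection reduces the point to a conflict between a parenthesis and a definition. It does not supply the missing outcome if Cohort 0 fails.

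**On the cap.** A reader might infer that the plan has no replacement policy. It does, in Section 2.2, whose trigger is a shortfall in evaluable patients, so the cap may have been meant that way. A cohort of three also has room under the cap. In addition, more than three doses missed for drug-related toxicity counts as a DLT, which keeps those patients evaluable. All of this narrows the problem, but the text still says enrolled.

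**On a firm ceiling under the listed levels.** Section 5.2.6.1 does not say whether a cohort cleared on three is filled to six after the next level is exceeded. With full back-filling down to Cohort 0, six levels could reach 6 × 6 + 10 = 46. The text does not spell this out, so 46 is not put forward as the plan's size; equally, no claim is made here that Cohort 0 cannot add to the total.

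**Conclusion.** The point holds as a minor internal inconsistency in four places.

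- The ceiling in Section 8.2.1 is 6 patients (15% of 40) below the one stated elsewhere.
- The MTD label conflicts with the plan's own DLT-based definition in the Cohort 0 branch. The 2.7% to 29.1% is the chance of reaching that branch at assumed DLT risks of 5% to 20%; it does not measure harm from the label.
- The enrolled cap conflicts with the replacement policy in an expanded cohort. The figures of at most 12%, 21% and 25% are maxima over the DLT risk at assumed non-evaluable rates of 10%, 20% and 30%. At lower DLT risks they are smaller.
- The dose-change target differs between sections and can affect membership of the efficacy population. The documents give no basis for a count.

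The probabilities assume independent patients. None of this shows that the trial would over-enrol or would adopt an MTD without data.

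**What to change.** 1. In Section 8.2.1, replace four levels and 34 with five levels and 40, to agree with the dose tables, the synopsis and Section 2.1.
2. In Section 5.2.6.1, reconcile the parenthetical label with the definition, so that the MTD follows from DLT results at that level. State what is reported if no level, including Cohort 0, qualifies. Also state whether a cohort cleared on three is filled to six after the next level is exceeded, since the ceiling depends on it.
3. State whether the limits of 6, 30, 10 and 40 count enrolled or DLT-evaluable patients, reconcile this with Section 2.2 for both phases, and give the total ceiling accordingly.
4. Reconcile the synopsis with Section 2.1 on the dose to which patients may change, and check the result against the population in Section 8.3.1. Which dose applies is for the sponsor to decide.

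The cost is wording. Patients are added only if the sponsor defines the cap in evaluable patients, in which case the ceiling must include replacements, or provides for back-filling beyond the present 40.
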